14.3.3 Rationale for Selected Analysis Method for the Primary Endpoint

It is believed, that applying the Bayesian progression model is an appropriate and powerful way of analysing MSA disease progression data in this context, since:

- The Bayesian methodology provides relatively simple computational and interpretable posterior probabilities for decision-making. In addition, it offers a robust performance in relation to convergence, as well as consistency across the performed analyses.
- There is a strong indication based on available 12-24 months MSA progression data¹ (i.e., UMSARS total and part I scores) of a steep and nearly linear disease progression trajectory; especially for the earlier patient segment, making it meaningful to talk about a change in the slope or a slowing down of progression.
- Due to the parametrization of effect expressed common across all visits, the model offers an easy interpretable target of estimation being the percentage-wise slowing in progression through up to 72 weeks treatment for Lu active dose compared to placebo.
- Based on the Lu AF82422 hypothesized mechanism of action, an early trend in UMSARS in favor of Lu AF82422 is reasonable due to the expected immediately steep MSA progression curve. Furthermore, the UMSARS is assessed for the first time at Week 12 following multiple dosing allowing time for initial treatment manifestation. Assuming that such an early trend will be further substantiated over time in a proportional-like manner due to the hypothesized moderation of the MSA pathology by Lu AF82422 (i.e., inhibition of seeding of pathological form(s) of alpha-synuclein, inhibition of the C-terminal proteolytic cleavage of alpha-synuclein, and potential immune-mediated clearance of alpha-synuclein/mAb complexes by the active Fc region), it seems less likely that the effect will significantly wear-off within the up to 72 weeks treatment period.
- The progression model is better suited for handling individual differences in treatment duration (i.e., when having differences in treatment duration due to the study design or a notable number of drop-outs/deaths); despite incomplete data (<72 weeks), a slope can still be estimated making full use of all patients. In particular, the long duration of the study (48-72 weeks) makes it more relevant to consider the effect integrated over time instead of the change from baseline for a single chosen timepoint.
- The progression model is well suited for handling also differences between visits due to the study design, where all ongoing patients will be called in for their respective end-of-treatment visit when the last patients randomized has completed 48 weeks of treatment.
- For treatment effect, the prior has been selected uniformly within [0, 2] for the active arms compared to placebo. In this way the prior is centred around no effect, i.e., $\theta_t = 1$, with $\theta_2 < 1$ referring to a slowing in progression, and $\theta_2 > 1$ referring to an increase.
- Remaining priors have been selected in a conservative and basically 'non-informative' manner by using relatively large outcome spaces. For the fixed effects of visit, β_j , a normal distributed prior centred around zero with a variance of 100 has been selected, since between-visit changes in the UMSARS scale can be both positive and negative with a relatively high variability. However, due to the rather aggressive disease progression observed within MSA, it is expected that the cumulated sums of β_j 's are positive leading to an interpretation of $\theta_2 < 1$ being an improvement.

Study 18331A - Statistical Analysis Plan

- For the subject-level effect a fairly simple parametrization has been selected by assuming these to be random with a uniformly shaped hyper-prior on the standard deviation within [0, 20]. In this way the covariance structure is assumed to be relatively simple.
- Since used for stratification, CCI and study region, respectively, will be accounted for by including as multiplicative fixed covariate effects parametrized on the logarithmic scale. For both parameters, a reference level will be set to zero and for the remaining level(s) a normally distributed prior will be selected centred around zero (for no difference) with a variance of 100. In this way the effect can go in either direction with little restriction on the size.
- The model has shown little bias in the treatment estimate for the selected scenarios. Additionally, under various formulations of the null hypothesis the model has with the chosen thresholds shown to adequately control the type 1 error on an overall 5% significance level evaluated 1-sided and has attractive type II error control under the alternative.
- It is already an established approach within other neurodegenerative diseases (e.g., AD²,³) and within diseases that cause progressive weakness and loss of muscle mass (e.g., Duchenne muscular dystrophy⁴ or GNE myopathy⁵) to model disease progression and show changes to expected disease deterioration as a change in the slope of progression.

To evaluate the appropriateness of the proposed progression model and the underlying assumptions, a number of sensitivity analyses will be conducted, incl. a MMRM to evaluate consistency across models especially in relation to how effect matures over time. Such approach will also be used to evaluate potential bias in effect estimates. See 14.3.5 Sensitivity Analyses of the Primary Endpoint for further details.

14.3.4 Evaluation of Model Assumptions for the Primary Analysis of the Primary Endpoint

The following goodness-of-fit diagnostics will be performed to assess the goodness-of-fit of the Bayesian primary repeated measures analysis:

- Residual plots for UMSARS TS: residuals vs. fitted values of UMSARS TS at each visit and for each treatment group.
- Mean and SD in change from baseline of UMSARS TS at each 12-week visit for each treatment group compared to model fitted expected values from primary analysis model.

14.3.5 Sensitivity Analyses of the Primary Endpoint

Handling of Missing Data

The following sensitivity analyses will be performed in case of drop-out/withdrawal/death, where the below rules will be applied for the visit following the event for subjects not having

complete data from the Withdrawal Visit, assuming that intermediate missingness will be 'missing at random':

- For withdrawal due to death, impute individual missing UMSARS items as worst possible score in case of death.
- For withdrawal due to other reasons, impute individual missing UMSARS items as worst observed within-subject value for the specific item at any post-IMP time point.
- For withdrawal due to other reasons, impute individual missing UMSARS items as the worst value observed within the combined treatment and control arms at any post-IMP time point.

Two analyses will be performed in both cases using the above strategy to handle withdrawal due death. Following each of the above strategies for handling withdrawals due to other reasons will then be applied.

To explore further the impact of death, a non-parametric joint-rank analysis will be performed to account for informatively missing data by ranking patients based jointly on their Week 48 UMSARS score (UMSARS TS and mUMSARS) and 48-week survival, i.e., time-to-death. Such analysis corresponds to a composite strategy. In case of missing Week 48 data for survivors, Multiple Imputation (MI) will be performed in which the remaining missing data will be imputed corresponding to a missing-at-random assumption.

Missing data for UMSARS Week 12 up to Week 48 will be addressed by using Multiple Imputation. Missing data will be imputed using a sequential regression-based multiple imputation method, based on the imputation models established from the corresponding randomized treatment group. Example SAS code for this imputation can be found in Appendix II.

200 imputed datasets will be created, which will each be analysed and combined as follow.

Define score, u_{ij} , which is chosen to reflect whether patient i has had the more favourable UMSARS score than patient j. In the case where both patient i and j died prior to the Week 48 assessment:

- $u_{ij} = 1$ in the case where patient i died after patient j
- $u_{ij} = -1$ in the case where patient i died before patient j
- $u_{ij} = 0$ in the case where it cannot be determined who died first

In the case where patient i died prior to the Week 48 assessment, and patient j has not died prior to the Week 48 assessment:

•
$$u_{ij} = -1$$

In the case where patient i did not die prior to the Week 48 assessment, and patient j died prior to the Week 48 assessment:

• $u_{ij} = 1$

In the case where both patient i and patient j are alive at Week 48 assessment:

- $u_{ij} = -1$ when UMSARS score for patient i at Week 48 > UMSARS score for patient j at Week 48
- u_{ij} = 1 when UMSARS score for patient i at Week 48 < UMSARS score for patient j at Week 48
- u_{ij} = 0 when UMSARS score for patient i at Week 48 = UMSARS score for patient j at Week 48

Using the u_{ij} for every pair of patients defined above, a score is assigned to each subject, $U_i = \sum_{i \neq j} u_{ij}$.

A t-test is applied to the U_i scores to compare the treatment groups. The estimated mean difference and associated SE from each of these analyses will be combined using Rubin's Rule. The p-value from this combined analysis will be presented.

Assumptions of Primary Efficacy Model

The following analyses will be conducted to test the sensitivity of the results to the primary efficacy model assumptions:

- The Bayesian repeated measures primary analysis model will be explored for sensitivity to priors by using a sceptical alternative for θ_2 , i.e., using a PERT distribution with mode 1.1 and a shape of 7.44 corresponding to a prior that Lu AF82422 is doing 60% worse than placebo.
- The UMSARS TS will be analysed using a restricted maximum likelihood (REML)-based mixed model for repeated measures (MMRM). The model will include the following: region, CCI and treatment (Lu AF82422 and placebo) as fixed factors, baseline UMSARS TS as continuous covariate, treatment-by-week interaction and baseline UMSARS TS-by-week interaction. An unstructured covariance structure will be used to model the within-patient errors. The Kenward-Roger approximation will be used to estimate denominator degrees of freedom. The analysis will be performed using all available observations (observed cases [OC] data) in the DBP. The estimated treatment differences between Lu AF82422 and placebo obtained at Week 48 will be estimated based on the least squares means for the treatment-by-week interaction in the MMRM model. Estimated treatment differences at Week 60 and 72 will be exploratory. In case of issues converging, a Toeplitz structure will be fitted instead.
- A constrained longitudinal data analysis with natural cubic splines that treats time as continuous, which allows separate splines for each treatment (Donohue et al, 2023)⁶. The natural cubic spline model assumes:

$$Y_{i,j} = \beta_0 + \sum_{k=1:m} (\beta_k \cdot b_k(t_j)) + Active_i \cdot \sum_{k=1:m} (\gamma_k \cdot b_k(t_j)) + \varepsilon_{ij},$$

Study 18331A - Statistical Analysis Plan

where $b_k(t)$ are the known spline basis functions for a given set of knots and extreme values of t, with Interior knots spaced according to quantiles of t. The resulting curve for the placebo group is defined by the natural cubic spline $f(t) = \beta_0 + \sum_{k=1:m} (\beta_k \cdot b_k(t_j))$; while the natural cubic spline $g(t) = \sum_{k=1:m} (\gamma_k \cdot b_k(t_j))$ represents the treatment group difference over time and is constrained to be zero at time zero. Estimation of the unknown parameters (β s and γ s) is accomplished with maximum likelihood estimation. It is to be noted, that a special case of the spline parameterization with visit times set to the planned times and knot locations chosen to match the planned visit times is equivalent with a categorical-time mean structure as found in the MMRM.

In this case, a natural spline with one interior knot at the median observation time has been selected as proposed by Donohue et al in their paper. In addition, as covariance matrix an unstructured approach will be applied. The model will in addition be adjusted for MSA sub-type and the two categorical covariates used for stratification, i.e., Region and CCI. The primary evaluation for the spline model will be performed at Week 48 and additional time points will be exploratory.

In fitting the model, the basis for the natural cubic splines is generated using the SAS® code given in the Appendix II.

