14.3 Analysis Methodology for the Primary Endpoint

14.3.1 Primary Analysis of the Primary Endpoint

The primary efficacy analysis following up to 72 weeks of treatment will be based on a Bayesian repeated measures model, also referred to as a Bayesian functional-impairment

progression model (BFPM), of the changes from baseline in the UMSARS TS. The BFPM incorporates the following aspects:

- Repeated measures for the change from baseline in the UMSARS TS score over the recurring 72-week's visit schedule
- Piece-wise linear rate of progression per 12-week time interval. However, does not require equally spaced intervals between observations. Time modelled continuously
- Patient-level random effect in rate of progression
- Proportional treatment effect, θ, for slowing of disease progression rate when treated relative to placebo. In particular, if θ<1, the active treatment slows the rate of progression relative to placebo. If θ>1, the active treatment increases the rate of progression relative to placebo. If θ=1, the rate of progression of UMSARS TS is the same for both active treatment and placebo
- Fixed multiplicative covariate effects in the increase or decrease in the overall rate of
 progression of UMSARS TS for categorized CCI

and region (US and Japan) common across all visits

- Prior distributions for model parameters selected in a conservative and non-informative manner using relatively large outcome spaces
- The primary analysis considers only actual observations and does not impute missing data

Let change from baseline in the UMSARS TS at visit *j* for subject *i* be labelled $Y_{i,j}$, $i = 1, ..., N, j = 1, ..., J_i$ where there are J_i total post-baseline visits for subject *i*. Change from baseline will be modelled as piece-wise linear with time intervals, k = 1, ..., K, defined every 12 weeks. Let $X_{i,j,k}$ be the exposure (time since baseline in weeks) for subject *i* at visit *j* during the time interval *k*. The MSA progression model is:

$$Y_{i,j} \sim N(\mu_{i,j}, \sigma_{t(i)}^2); i = 1, ..., N; j = 1, ..., J_i$$

$$\mu_{i,j} = 0 + \sum_{k=1:K} \left(\beta_k + \beta_{k,i} \right) * (X_{i,j,k}/12) * \theta_{t(i)} * \exp\left(\delta_{g(i)} + \eta_{r(i)} \right)$$

where each parameter is defined below and the prior distribution for the parameter is given:

 β_k : Mean expected change from baseline over each 12-week interval

$$\beta_k \sim Norm(0, 10^2)$$
; $k = 1, \dots, K$

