14.3.7 Covariate Analyses of the Primary Endpoint

The effect of covariates on the primary endpoint will evaluated applying an ANCOVA to the change from baseline to Week 48 in UMSARS TS including the baseline UMSARS TS, Region, and CCI. The following covariates will be added and evaluated once at a time:

- age (categorized as <50yrs; 50-60; >60yrs)
- gender (female/male)
- race
- time-since-symptom onset (as yearly intervals)

- baseline plasma/CSF alpha-synuclein and CSF NfL (defined as baseline lower/middle/upper tertile)
- baseline disease severity according to category of CGI-S and UMSARS part IV (global disability score 1-5), and SE-ADL (defined as baseline lower/middle/upper tertile)

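### The joint-rank analysis of death (SAP 14.3.5) compares U_i by an unadjusted t-test, which is valid on average but can lose precision and carries any chance baseline difference into the result

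*SAP*

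**What the plan says.** SAP 14.3.5 adds a non-parametric analysis to explore the impact of death, "ranking patients based jointly on their Week 48 UMSARS score (UMSARS TS and mUMSARS) and 48-week survival". A patient who died before Week 48 scores worse than any survivor, and an earlier death scores worse than a later one. For two survivors the raw values are compared: u_ij is -1 "when UMSARS score for patient i at Week 48 > UMSARS score for patient j at Week 48". The u_ij are summed to U_i, and a plain t-test is run on these "scores to compare the treatment groups. The estimated mean difference and associated SE from each of these analyses will be combined using" the standard pooling rule (Rubin's), over 200 imputed datasets. No covariate is named. SAP 14.4.1 sets up the mUMSARS sensitivity analyses in a similar way.

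The other UMSARS TS analyses all use baseline:

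- Primary model (SAP 14.3.1): "Repeated measures for the change from baseline in the UMSARS TS score over the" 72-week schedule. On the strata, SAP 14.3.3 says: "Since used for stratification, CCI and study region, respectively, will be accounted for by including as multiplicative fixed covariate effects".
- MMRM (SAP 14.3.5): region and the other stratification factor, with "baseline UMSARS TS as continuous covariate, treatment-by-week interaction and baseline UMSARS TS-by-week interaction".
- Spline model (SAP 14.3.5): its second spline "represents the treatment group difference over time and is constrained to be zero at time zero", and the model is also adjusted for sub-type and both stratification factors.
- Covariate analyses (SAP 14.3.7): "applying an ANCOVA to the change from baseline to Week 48 in UMSARS TS including the baseline UMSARS TS, Region" and the other stratification factor.

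**The concern.** A raw Week 48 score is the baseline score plus the change. Ranking on it brings the spread of baseline severity into U_i, and a plain t-test does not take it out again. Two things follow. Noise from starting severity can hide a treatment difference. And if one arm happens to start worse, that difference feeds straight into the estimate.

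The analysis exists to show whether the primary result holds up once deaths are counted. If it disagreed with the primary analysis, a reader could not tell from it alone whether mortality or starting severity was the cause. Adjusting after unblinding would look post hoc.

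**Working it through.** **Inputs from the documents.** 40 v 20 patients, 40% slowing, one-sided 5%, about 75% power for the repeated-measures model (Protocol 17.12, SAP 21). The SAP sets no threshold for the joint-rank analysis, so one-sided 5% is only a yardstick here.

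**The plan's own figure.** No power is stated for the joint-rank test. The 75% comes from a simulation with drop-out whose progression rate and SD are not in the public text, so it cannot be rebuilt. It can be back-solved for a two-group comparison: d = (1.645 + 0.674) × √(1/40 + 1/20) = 2.319 × 0.274 = 0.635 SD. With an assumed placebo change of 12 points, 40% slowing gives 7.2 on active, an effect of 4.8 and a change SD of 4.8/0.635 = 7.56. A t-test on change then has 74% power.

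**Chance imbalance.** The SE of the baseline difference is SD × √(1/40 + 1/20) = 0.274 baseline SDs. If the baseline SD equals the change SD, that is 0.274 × 7.56 = 2.1 points, against an effect of 4.8.

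**Why the raw score costs precision.** Let r be baseline SD / change SD and c the baseline-change correlation, both assumed. Relative to the variance of change:

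- raw Week 48 score: 1 + r² + 2cr
- Week 48 score adjusted for baseline: 1 − c²

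At r = 1, c = 0 these are 2 and 1. At r = 0.5, c = 0 they are 1.25 and 1. At r = 0.5, c = −0.3 they are 0.95 and 0.91, so there is almost nothing to recover. The raw score loses nothing against change itself once c ≤ −r/2.

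**Simulated power on U_i.** The full ANCOVA has treatment, baseline, region and a three-level second factor (low, high and missing, as in SAP 14.3.1). Assumed: 25% Japan, 10% missing, neither factor prognostic; deaths equal in both arms and unrelated to baseline; no missing data and so no imputation step. There were 2,500 trials per cell, with a Monte Carlo SE of about 1 point.

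| r, c | Deaths | t-test | Full ANCOVA |
|---|---|---|---|
| 0.5, 0 | 0% | 63% | 69% |
| 0.5, 0 | 5% | 56% | 60% |
| 0.5, 0 | 10% | 48% | 50% |
| 1, 0 | 0% | 48% | 68% |
| 1, 0 | 5% | 39% | 53% |
| 1, 0 | 10% | 34% | 42% |
| 0.5, −0.3 | 0% | 73% | 73% |
| 0.5, −0.3 | 5% | 65% | 64% |
| 0.5, −0.3 | 10% | 59% | 57% |

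**Type I error.** A larger run (20,000 trials per cell, second factor taken as binary) gave overall null rejection of 4.6 to 5.4% for every analysis.

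**Given an imbalance of about 1 SE** (same larger run, no deaths, c = 0):

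- Power at r = 1, active arm starting worse: t-test 16%, ANCOVA 68%.
- Power at r = 1, active arm starting better: t-test 81%, ANCOVA 69%.
- Null rejection over ratios 0.5 to 1.5: t-test 0.0 to 1.0% (active worse) or 8.5 to 9.4% (active better); ANCOVA 4.1 to 6.0%.

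These figures are for UMSARS TS. mUMSARS was not sized.

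**The case against.** No decision rests on this analysis. It is exploratory, has no success rule and lies outside the fixed sequence of SAP 15.2. Death is also covered by two worst-score imputation analyses (SAP 14.3.5) and by a Kaplan-Meier plot with, if applicable, a Cox model (SAP 16.9). Baseline-adjusted Week 48 comparisons already exist in the MMRM, the spline model and the 14.3.7 ANCOVA, so a reader can check there whether imbalance mattered. Protocol 17.9.3 plans a non-parametric rank analysis and mentions no adjustment; keeping one model-light check among several adjusted models is defensible. The gains are largest with no deaths, which is where the analysis matters least. The deciding quantities (baseline SD, change SD, their correlation) are not in the documents, and the Part I limit of 16 at screening restricts baseline spread.

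All of this stands as a limit on weight. It does not remove the point: the adjusted models do not include the death ranking, and the one analysis that does leaves out a baseline value already collected.

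A reader might infer more than the documents support:

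- **That the t-test is invalid or inflates type I error.** Over all randomisations it does not. The distortion is conditional on the imbalance that happens to occur, so calling the test unbiased is right only on average.
- **That the primary conclusion is at risk.** It rests on the Bayesian model of change, which this analysis does not touch.
- **That the SAP departs from the protocol by not adjusting.** Protocol 17.9.3 names no test, so neither a t-test nor an ANCOVA contradicts it.
- **That adjustment always helps.** At r = 0.5, c = −0.3 it does not.

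**Conclusion.** The point holds as a cheap improvement of the lowest severity. The unadjusted comparison of U_i is valid on average but exposed to chance baseline differences, and it is out of line with how the SAP treats baseline in its other UMSARS TS models.

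With baseline unrelated to change, the assumed gain from the full ANCOVA runs from 2 points (r = 0.5, 10% deaths: 48 to 50%) to 20 points (r = 1, no deaths: 48 to 68%). With r = 0.5 and c = −0.3 it is nil to slightly negative. Which case applies depends on SDs and a correlation that the documents do not give.

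Baseline is the essential term. Stratified randomisation already limits imbalance in region and the other factor, so those terms add precision only as far as they are prognostic. Even after the change, this analysis may differ from the primary result because of its single time point, rank scale and composite handling of death.

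**What to change.** In SAP 14.3.5, replace the t-test sentence with text such as: *An ANCOVA will be fitted to the U_i scores with treatment, the baseline value of the score being ranked, region and the other stratification factor (three levels, including missing). The adjusted mean difference and its SE from each imputed dataset will be combined by Rubin's Rule. The unadjusted t-test will be shown beside it.* Leave the u_ij rules as they are, and apply the same text to mUMSARS. If a shorter model is preferred, keep baseline and make the stratification terms optional.

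The cost is one model statement on data already collected, plus about 2 power points if the stratification factors turn out not to be prognostic. Ranking survivors on change from baseline could be added as a supplementary output. It answers a slightly different question from the score ranking in Protocol 17.9.3, so it is optional. The change should be made before unblinding.
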